2.7.1.2 Optical coherence Tomography (OCT)

The following secondary efficacy parameters based on OCT will be analyzed as given below.

2.7.1.2.1 Central sub-field retinal thickness (CSFT)

The summary statistics of central sub-field retinal thickness (CSFT) measured by OCT for nAMD patients, change and percentage change from Baseline in CSFT will be presented by visit along with first anti-VEGF Treatment CSFT.

The number and percentage of patient with CSFT category (< 300 , $\geq 300 - 450$, $\geq 450 - < 650$, ≥ 650 [μm]) will be presented by visit along with first anti-VEGF Treatment CSFT.

The above analysis will be done on the FAS and only on the study eye.

2.7.1.2.2 Presence of fluid (Yes/No)

The number and percentage of patients with fluid as shown below will be presented by visit along with first anti-VEGF Treatment.

1. Intraretinal fluid
2. Subretinal fluid
3. Sub-RPE fluid
4. Without any fluid (IRF/SRF/sub-RPE)
5. In case of sub-RPE / PED : nature : (serious PED/fibrovascular PED/mixed PED)

Volume (mm^3) and height (μm) of intraretinal fluid, subretinal fluid and/or sub-RPE fluid will be presented the summary statistics (n, mean, std, median, min and max) by visit, if available.

The above analysis will be done on the FAS and only on the study eye.

2.7.1.2.3 Dry retina

The proportion of patients without both fluids (IRF and SRF), without IRF, without SRF, without sub-RPE will be presented by visit, separately, up to Week 48/Week 50.

The proportion of patients without fluid (IRF and SRF) and having fluid (IRF and/or SRF) in entire study will be presented.

The 95% confidence interval (CI) for proportion using the Clopper-Pearson method will be provided by visit and overall.

The above analysis will be done on the FAS and only on the study eye.

2.7.1.2.4 Time to dryness

The median time to dryness will be obtained from Kaplan-Meier (KM) analysis along with 2 sided 95% CI will be presented. KM plot will be provided. Details KM result will be presented including time (week), number of patients under at risk at week (without dry retina), number of patients with dry retina at week (event), probability of dry retina (survival probability) at week and 95% CI at week.

Variable	Definition
Start date	Start date of IVT injection
Event	Dry retina (absence of IRF and/or SRF)
End date of event	Start date of first dry retina
Censoring (end date)	Earliest of: Absence of dry retina until EOS Early discontinuation without dry retina
Duration of time	(End date – start date) +1

The above analysis will be done on the FAS and only on the study eye.

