1.2 Purpose

The purpose of this study is to assess both early (at Week 16 just after the loading phase) and long-term (48 weeks) effects of brolucizumab on disease control in suboptimal anatomically controlled nAMD patients.

2 Objectives and endpoints

Table 2-1 Objectives and related endpoints

Objectives	Endpoints
Primary objective	Endpoint for primary objective

To evaluate the effect of brolucizumab 6 mg on disease control	
Proportion of patients with no disease activity at Week 16
Secondary objectives	Endpoints for secondary objectives

To evaluate the long term effects of brolucizumab 6 mg on disease control	
Proportion of patients with no disease activity at Week 48

To evaluate the effect of brolucizumab 6 mg on anatomical parameters	
Change from Baseline in CFST as assessed by OCT over time up to Week 48Absence of IRF, SRF, and sub-RPE fluid as assessed by OCT over time up to Week 48Proportion of patients with a dry retina (neither IRF nor SRF) up to Week 48

To evaluate the durability of brolucizumab 6 mg	
Distribution of the last interval with no disease activity up to Week 48Distribution of the maximal intervals with no disease activity up to Week 48

Objectives	Endpoints

To evaluate functional outcomes	
Average change in BCVA from Baseline up to Week 48

To assess the safety and tolerability of brolucizumab 6 mg	
Incidence of AEs (serious and non-serious) up to Week 48

AEs=adverse events, BCVA=best corrected visual acuity,
retinal thickness, [REDACTED]

CSFT=central sub-field
IRF=intraretinal fluid, OCT= optical coherence tomography, [REDACTED]
SRF= subretinal fluid

3 Study design

This is a prospective, single-arm, open-label, multicenter study to evaluate the efficacy and safety of brolucizumab 6 mg in pretreated suboptimal anatomically controlled patients with nAMD.

Approximately 295 adult patients will be screened and included (10% dropout rate expected) in France.

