12.5.2 Effect of brolucizumab 6 mg on anatomical parameters

Summary statistics of the change from Baseline in CSFT up to Week 48 will be provided.

The number (%) and proportion of subjects with absence of IRF, SRF, and sub-RPE fluid as assessed by OCT over time up to Week 48 will be presented.

The number (%) and proportion of subjects with dry retina (no IRF nor SRF) up to Week 48 will be presented.

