1.2 Study objectives and endpoints

Table 2-1 Objectives and related endpoints

Objectives	Endpoints
Primary objective	Endpoint for primary objective
• To evaluate the effect of brolucizumab 6 mg on disease control	• Proportion of patients with no disease activity at Week 16
Secondary objectives	Endpoints for secondary objectives
• To evaluate the long term effects of brolucizumab 6 mg on disease control	• Proportion of patients with no disease activity at Week 48
• To evaluate the effect of brolucizumab 6 mg on anatomical parameters	• Change from Baseline in CSFT as assessed by OCT over time up to Week 48 • Absence of IRF, SRF, and sub-RPE fluid as assessed by OCT over time up to Week 48 • Proportion of patients with a dry retina (neither IRF nor SRF) up to Week 48
• To evaluate the durability of brolucizumab 6 mg	• Distribution of the last interval with no disease activity up to Week 48 • Distribution of the maximal intervals with no disease activity up to Week 48
• To evaluate functional outcomes	• Average change in BCVA from Baseline up to Week 48
• To assess the safety and tolerability of brolucizumab 6 mg	• Incidence of AEs (serious and non-serious) up to Week 48

AEs=adverse events, BCVA=best corrected visual acuity, [REDACTED] CSFT=central sub-field retinal thickness, [REDACTED] IRF=intraretinal fluid, OCT= optical coherence tomography, [REDACTED]
SRF= subretinal fluid.

2 Statistical methods

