Percent change from Baseline: The percent change from baseline will be calculated as below: $((\text{post-baseline value} - \text{Baseline value}) / \text{Baseline value}) * 100$.

Proportion: A proportion refers to the fraction of the total that possesses a certain attribute. In this study attribute is disease free activity.

Disease control: When patients have no disease activity after taking study treatment then patient will be consider as disease control.

On-treatment period: The on-treatment period lasts from the date of first administration of study treatment to 30 days after the date of the last actual administration of any study treatment.

Treatment duration: The maximum planned duration of treatment for each patient is 44 to 46 weeks in accordance with the designated treatment regimen. Discontinuation of study treatment for a patient occurs when study treatment is stopped earlier than the protocol planned duration and can be initiated by either the patient or the investigator.

Treatment discontinuation: When patients discontinue study treatment but continue in the study, the efficacy data will be used at the time the patient stopped study treatment.

Last interval: The last treatment interval (defined by the investigator) before Week 48.

Maximum interval: The longest interval of treatment reached by the patient over the study period.

Event for no disease activity: When patients will be with no disease status as per investigator decision after last dose in initiation phase then the patients will consider as event for no disease activity. If patients with active disease status or early discontinue then patients will be considered as censored for disease activity.

Dry retina: Absence of fluid (IRF/SRF/ sub-RPE) will be considered as dry retina.

Event for dry retina: When patients have absence of fluid then it will be considered as an event of dry retina. If patients have a presence of fluid before/at EOS or early discontinuation then will be censored.

[figure not shown]
Study eye and fellow eye: The investigator selects the eye with the worse BCVA at Screening as the study eye if both eyes are eligible as per the inclusion and exclusion criteria, unless the investigator deems as a study eye more appropriate to select the eye with better BCVA, based on medical reasons or local ethical requirements. If both eyes are eligible as per the inclusion and exclusion criteria, then it is recommended to select the right eye as the study eye.

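### Dry retina is defined inconsistently, the time-to-dryness event can be read as already met at baseline, and its survival probability carries the opposite label

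*SAP*

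**What the plan says.** The documents describe a dry retina in three ways.

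- **Neither IRF nor SRF.** Protocol Table 2-1 has "dry retina (neither IRF nor SRF) up to Week 48", Protocol 12.5.2 has "dry retina (no IRF nor SRF) up to Week 48", and the SAP's own endpoint table (1.2) has "Proportion of patients with a dry retina (neither IRF nor SRF) up to Week 48".
- **Sub-RPE fluid added.** SAP 2.1.1 states: "Absence of fluid (IRF/SRF/ sub-RPE) will be considered as dry retina".
- **And/or.** SAP 2.7.1.2.4 gives the time-to-dryness event as "Dry retina (absence of IRF and/or SRF".

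SAP 2.7.1.2.4 starts the clock at the injection and dates the event at the first dry retina, without restricting it to post-baseline visits. It counts eyes without dry retina as at risk. The results table is to show "probability of dry retina (survival probability) at week and 95% CI at week". Censoring covers eyes still not dry at end of study and "Early discontinuation without dry retina".

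Entry requires IRF or SRF in the central subfield (Protocol 5.1, criterion 5), so one type is enough. The subgroups in SAP 2.6.2 list IRF, SRF and both as separate baseline categories. SAP Section 4 declares no change to the protocol-specified analyses.

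**The concern.** A definition that varies between sections leaves the programmer to choose, and the choices give different results. Under the and/or wording, an eye that entered with only one fluid type lacks the other from the start and so qualifies as dry before the drug has acted. Under SAP 2.1.1, an eye with only sub-RPE fluid is not dry, although it is dry under the protocol endpoint.

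Separately, when dryness is the event, the Kaplan-Meier survival function falls as eyes dry. Labelling it as the probability of dryness makes a good result look poor and a poor one look good.

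At stake are the median time to dryness, the Kaplan-Meier table and the legibility of the plot.

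**Working it through.** The plan states no expected time to dryness, so there is no figure to reproduce. The check compares the definitions and then applies the Kaplan-Meier identity.

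**1. Definitions side by side**

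| Fluid present | Neither IRF nor SRF (protocol) | SAP 2.1.1 | SAP 2.7.1.2.4, literal |
|---|---|---|---|
| IRF only | not dry | not dry | dry |
| SRF only | not dry | not dry | dry |
| IRF and SRF | not dry | not dry | not dry |
| Sub-RPE only | dry | not dry | dry |
| None | dry | dry | dry |

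The first two rows are eyes that may be enrolled. Under the literal reading both are events at time zero. With the SAP's duration formula (end minus start, plus 1), such an eye scores 0 + 1 = 1 day if injected on the baseline date. If the injection follows 3 days after the visit, as Protocol Section 3 permits, it scores -3 + 1 = -2 days.

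Excluding the baseline visit would not by itself cure this. A single-fluid eye would become an event at its first later visit unless the other fluid had appeared by then.

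**2. Effect on the median (illustration; inputs assumed)**

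Let s be the share of eyes with one fluid type at baseline, and F(t) the cumulative proportion reaching neither IRF nor SRF. Under the literal event the cumulative proportion is at least s + (1 - s) × F(t). This is a lower bound, because an eye with both fluids meets the literal event as soon as one clears. Assume F = 0.30, 0.45, 0.55 and 0.65 at Weeks 4, 8, 16 and 48, with no early censoring.

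- Protocol definition: F passes 0.50 between Week 8 (0.45) and Week 16 (0.55), so the median is Week 16.
- s = 0.30: 0.30 at baseline and 0.30 + 0.70 × 0.30 = 0.51 at Week 4, so the median is Week 4.
- s = 0.50: 0.50 at baseline (0.50 × 295 = 147.5 eyes), so the median is at baseline.
- s = 0.90: 0.90 at baseline (0.90 × 295 = 265.5 eyes), so the median is at baseline.

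The threshold of about 50% for a baseline median does not depend on the assumed F. The Week 4 and Week 16 results do.

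**3. The label**

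With dryness as the event, S(t) is the probability of not yet being dry, and the probability of having dried by t is 1 - S(t). For 295 eyes and the same assumed curve, new dry eyes number 88, 45, 29 and 30 at Weeks 4, 8, 16 and 48:

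- S(4) = 207/295 = 0.702
- S(8) = 162/295 = 0.549
- S(16) = 133/295 = 0.451
- S(48) = 103/295 = 0.349

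About 65% have dried by Week 48, while the column headed probability of dry retina would read about 35%. The sample code in SAP 5.4 contains no step to 1 - S(t).

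**4. Maximum duration of dryness (SAP 2.7.1.2.5)**

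Here the clock runs from start to end of dryness, so S(t) is the probability of still being dry and that label is sound. The other labels are reversed. The at-risk set is described as eyes with fluid and the event as dryness, whereas the eyes at risk are dry and the event is the return of fluid.

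**The case against.** Several points on the other side stand.

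- **Intent.** The authors probably meant both fluids absent. The SAP endpoint table says so, and SAP 2.7.1.2.3 uses and/or only for having fluid: "The proportion of patients without fluid (IRF and SRF) and having fluid (IRF and/or SRF) in entire study will be presented". That is the correct complement of the protocol definition, and 2.7.1.2.4 may have carried the phrase to the wrong side. A reader might infer that following the SAP must produce a Day 1 median. The documents do not support that: it needs the literal reading and a single-fluid share of about half or more. What stands is that 2.7.1.2.4 does not settle the matter and could be coded either way.
- **Importance.** A reader might infer that a listed endpoint is wrong. Time to dryness is not in Protocol Table 2-1 or the SAP endpoint table, and the interim plan marks it not applicable. SAP 2.7.1.2.3 reports eyes without IRF and SRF, and sub-RPE fluid separately, so the protocol's proportion is produced whatever 2.1.1 says.
- **Label.** The words in parentheses identify the quantity, the median is unaffected, and table shells not available here may use a better heading. The text as written is still wrong.
- **Censoring.** A reader might infer that the curve is biased because eyes stopped while wet are censored. The link is plausible, since IRF or SRF due to disease activity is itself an activity criterion and activity at Week 14 ends study treatment. But the documents do not say how many eyes would stop wet, and no OCT is scheduled after the early-discontinuation visit (Protocol Table 8-1). Protocol 12.4.3, written for the primary endpoint, also censors at the end of treatment. Counting such eyes as not dry answers a different question, so this supports a sensitivity analysis at most.

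**Conclusion.** The definitions conflict, and the SAP does not acknowledge the difference. Read literally, the time-to-dryness event is met at entry by every single-fluid eye. The median could then fall as early as baseline, which requires a share of about 50% or more. The share is unknown. Over an assumed range of 30% to 90%, the illustrative median moves from Week 16 under the protocol definition to Week 4 at 30% and to baseline from 50% upwards.

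The label error holds on any definition: with no censoring, 35% would be shown where 65% have dried.

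The reach is limited to supportive Kaplan-Meier analyses of a secondary objective. The primary endpoint is not involved, and the listed dry-retina proportion is already specified as the protocol intends. The correction should be made because the rules as written can yield a wrong event date and a misread probability column.

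**What to change.** - In SAP 2.1.1 and 2.7.1.2.4, define dry retina as neither IRF nor SRF. Section 2.7.1.2.3 needs no change. Absence of all three fluids can remain as the separate row in 2.7.1.2.2.
- In 2.7.1.2.4, count events only from the first post-baseline visit. This is worth stating even under the protocol definition: the investigator judges eligibility while the reading centre supplies the OCT endpoint data (Protocol 8.3.1), so an enrolled eye could be graded dry at baseline.
- Report 1 minus the Kaplan-Meier estimate as cumulative dryness, or relabel S(t) as the probability of not yet being dry.
- In 2.7.1.2.5, describe the at-risk set as dry eyes and the event as the end of dryness.
- Optionally, add a sensitivity analysis that keeps eyes stopped while wet as not dry to the end of the planned period.

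The cost is SAP wording and programming. No new data are needed.

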For all patients completing the study as per protocol, the End-of-Study (EOS) assessment will be performed at Week 48 (or Week 50 for patients receiving their last treatment at Week 46), at least 4 weeks (\pm 7 days) following the last possible study treatment administration. For patients who receive their last IVT at Week 46, the EOS assessment will be performed at Week 50 (\pm 7 days), at least four weeks (\pm 7 days) following their last possible study treatment administration. For clarity reason, the EOS visit will be named Week 48 in the rest of this protocol.

Patients withdrawn from the study prior to study completion will be asked to return for an early discontinuation (EOS) visit, 4 weeks (\pm 7 days) following their last study treatment administration. For early treatment discontinuations (ETD) refer to [Section 9.1.1](#).

4 Rationale

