6.7.2.2 Treat-to-Control Phase

After the Initiation Phase, the Treat-to-Control Phase will start from Week 8, where the injection interval will be extended by 4 weeks to Week 16 (according to disease activity).

The Treat-to-Control Phase rules are defined as follows:

- Following Week 8, treatment intervals will be either 8 weeks, 12 weeks, or 16 weeks. A patient must be discontinued from further study treatment if treatment is required more frequently, i.e., every 4 weeks.
- The assessment of disease activity will be performed at each visit by the Investigator.
- At Week 8, based on Investigator's judgment of visual and/or anatomic outcomes, treatment intervals will be extended by 4 weeks at a time, if there is no disease activity, i.e. no change in visual acuity and in other signs of the disease (e.g. IRF, SRF, hemorrhage, leakage, etc.). From Week 16, the injection interval can be maintained on Q8 (or Q12 from Week 28) if the Investigator deems that the patient will not benefit from treatment interval extension, with a minimal interval of 8 weeks.
- If disease activity recurs, treatment intervals should be shortened accordingly by 4 weeks at a time or to a minimal interval of 8 weeks.
- At the Investigator's discretion, an inspection visits at Week 14, i.e. 6 weeks after the 3rd injection, can be performed. If there is no disease activity in the study eye at Week 14, as assessed by the Investigator, the study treatment will not be administered; the next visit and injection will take place at Week 16. If disease activity is observed by the Investigator in the study eye at Week 14, the study treatment will be administered by the Investigator, and the subject will be discontinued from further study treatment.
- Inspection visits 10 weeks after the last injection can be performed at the Investigator's discretion when the injection interval is extended from 8 weeks to 12 weeks. If there is no disease activity in the study eye at the inspection visit as assessed by the Investigator, the study treatment will not be administered; the next visit and injection will take place 2 weeks later, i.e. 12 weeks after the previous study treatment. If disease activity is observed by the Investigator in the study eye at the inspection visit, the study treatment will be administered by the Investigator; the injection interval will be reduced to 8 weeks and the next injection visit will be 8 weeks after the inspection visit.

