9.1 Discontinuation

9.1.1 Discontinuation of study treatment

Discontinuation of study treatment for a patient occurs when study treatment is stopped earlier than the protocol planned duration and can be initiated by either the patient or the Investigator.

The Investigator must discontinue study treatment for a given patient if he/she believes that continuation would negatively affect the patient's well-being.

The Investigator and/or referring physician will recommend the appropriate follow-up medical care, if needed, for all patients who are prematurely withdrawn from the study.

Study treatment must be discontinued under the following circumstances:

- Patient requires treatment on a q4w interval after the initiation phase (Week 14/Week16), i.e., after the three-monthly injections at Baseline, Week 4, and Week 8, followed by the first interval extension

- Patient develops intraocular inflammation, including retinal vasculitis and/or retinal vascular occlusion
- Patient/guardian decision
- Pregnancy
- Use of prohibited treatment
- Any situation in which study participation might result in a safety risk to the patient

If premature discontinuation of study treatment occurs, the following should be done as appropriate:

- The Investigator should make a reasonable effort to understand and document the primary reason for the patient's premature discontinuation of study treatment using the appropriate eCRF page.
- Patients who prematurely discontinue study treatment for any reason should return 4 weeks after last study treatment to perform the assessments for early treatment discontinuation (ETD). Please refer to [Table 8-1](#), except for patients who withdraw their consent from the study and do not wish to do so (refer to [Section 9.1.2](#)).
- After these assessments are performed, patient can be switched to standard of care (SOC) anti-VEGF IVT as per investigators discretion. IVT injection is contraindicated in patients with active intraocular or periocular infections and in patients with active intraocular inflammation; therefore, the investigators must verify that these conditions are not present in the study eye prior to every injection.
- After premature study treatment discontinuation, at a minimum till week 48, in abbreviated visits, the following data should be collected at clinic visits or via telephone/email contact:
 - New/concomitant treatments
 - Adverse events/Serious Adverse Events
 - BCVA

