12.4.3 Handling of missing values/censoring/discontinuations

For patients who:

- Discontinue study treatment but continue in the study, the efficacy data will be censored at the time the patient stopped study treatment in the study eye.
- Interrupt treatment, the efficacy data will be censored at the time the study treatment was first interrupted.

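### Time to dryness censors still-wet eyes at an undefined early discontinuation; if that means stopping treatment, the Kaplan-Meier curve sits at or above the true share of eyes drying on brolucizumab

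*SAP*

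**What the plan says.** SAP 2.7.1.2.4 plans a Kaplan-Meier median with 95% CI, a plot and a week-by-week probability of dry retina, in study eyes of the FAS. The event is the first dry retina. An eye that never dries is censored at EOS or at "Early discontinuation without dry retina". The dry-retina event definition in SAP 2.1.1 matches: "If patients have a presence of fluid before/at EOS or early discontinuation then will be censored". Neither place says what is being discontinued.

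The protocol points both ways. Section 12.4.3, written for the primary endpoint, says that for patients who stop treatment but stay in the study "the efficacy data will be censored at the time the patient stopped study treatment in the study eye". Section 3 (Follow-up Period) instead attaches the phrase to study withdrawal: withdrawn patients "will be asked to return for an early discontinuation (EOS) visit", while a treatment stop is called ETD.

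Stopping is partly driven by disease activity:
- Protocol 9.1.1 requires it when "Patient requires treatment on a q4w interval after the initiation phase", and also for intraocular inflammation, retinal vasculitis or retinal vascular occlusion.
- Protocol 6.7.2.2 adds that, if activity is seen at the optional Week 14 inspection visit, "the study treatment will be administered by the Investigator, and the subject will be discontinued from further study treatment".
- Other recurrent activity does not force a stop. In that case "treatment intervals should be shortened accordingly by 4 weeks at a time or to a minimal interval of 8 weeks".

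Table 8-1 includes OCT at the ETD visit. Its post-ETD column has BCVA, adverse events and medications but no OCT, and footnote 16 waives the Week 16 and Week 48/50 visits. After the ETD assessments the eye may move to standard-of-care anti-VEGF (Protocol 9.1.1).

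**The concern.** Kaplan-Meier assumes that an eye censored at a given week has the same later chance of drying as an eye still under observation. An eye stopped because it needs q4w injections, or is active at Week 14, is unlikely to meet that assumption. SAP 2.1.1 lists IRF or SRF due to disease activity among the signs of active disease, and freedom from IRF and SRF is what time to dryness counts. The reason for censoring and the outcome therefore overlap.

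Once the ETD visit has passed, first dryness on brolucizumab can no longer be observed, so stopping while wet acts as a competing event. Censoring it instead gives the stopped eyes the drying rate of eyes that did well enough to continue. The reported probability of dry retina may then be read as the share of eyes that dried, and in some scenarios a median is reported although fewer than half of the eyes ever dried. SAP 2.7.1.2.4 plans no competing-risk or sensitivity analysis.

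**Working it through.** **Plan's own figure.** There is none for time to dryness. The nearest planning value is 25% to 35% of patients with no disease activity at Week 16 (Protocol 12.8), a different quantity, used here only as a proxy range for early dryness. N = 295 comes from the same section.

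**Which reading.** Treatment stop is the more natural one: Protocol 12.4.3 censors efficacy data there, and scheduled OCT ends at ETD. The wording in Protocol Section 3 keeps study withdrawal possible.

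**Model, treatment-stop reading.** Three assumed inputs:
- d: share of eyes dry before the stops
- f: share of still-wet eyes stopped at about Week 14 to 18
- g: share of continuing wet eyes that dry by Week 48

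Stopped eyes remain in the denominator as not dried on brolucizumab. Then:
- 1 − KM = 1 − (1 − d)(1 − g)
- cumulative incidence = d + (1 − d)(1 − f)g
- excess = (1 − d)·f·g, which is never negative

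For the medians, later drying is spread with equal hazard over Weeks 24, 32, 40 and 48. After k of these visits, g is replaced by 1 − (1 − g)^(k/4).

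| d | f | g | 1 − KM | Cumulative incidence | Excess (points) | Median, KM / cumulative incidence |
|---|---|---|---|---|---|---|
| 0.30 | 0.10 | 0.40 | 58.0% | 55.2% | 2.8 | Week 40 / Week 40 |
| 0.30 | 0.25 | 0.40 | 58.0% | 51.0% | 7.0 | Week 40 / Week 48 |
| 0.30 | 0.50 | 0.40 | 58.0% | 44.0% | 14.0 | Week 40 / not reached |
| 0.60 | 0.25 | 0.40 | 76.0% | 72.0% | 4.0 | Week 16 / Week 16 |
| 0.60 | 0.50 | 0.60 | 84.0% | 72.0% | 12.0 | Week 16 / Week 16 |

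**Range.** For d = 0.25–0.35, f = 0.10–0.50 and g = 0.20–0.60:
- smallest excess: 0.65 × 0.10 × 0.20 = 1.3 points
- largest excess: 0.75 × 0.50 × 0.60 = 22.5 points

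At d = 0.60 with the same f and g, the excess runs from 0.40 × 0.10 × 0.20 = 0.8 to 0.40 × 0.50 × 0.60 = 12.0 points. At f = 0 it is zero.

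**Against sampling error.** With N = 295 and d = 0.30, using the Greenwood SE of 1 − KM:
- f = g = 0.50: 65.0% against 47.5%, a gap of 17.5 points with SE 3.7, or 4.7 SE
- f = 0.25, g = 0.30–0.50: 5.3 to 8.8 points, or 1.6 to 2.8 SE
- f = 0.10, g = 0.30–0.50: 2.1 to 3.5 points, or 0.7 to 1.2 SE

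**If the target is drying had treatment continued.** Let g′ be the chance that stopped eyes would have dried. The excess becomes (1 − d)·f·(g − g′). With d = 0.30, f = 0.25 and g = 0.40 it is 7.0 points at g′ = 0, 3.5 at g′ = 0.20 and zero at g′ = 0.40.

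**Study-withdrawal reading.** Eyes stopped for activity stay at risk to EOS and most of this bias goes. They are then at risk without scheduled OCT, and a discretionary scan showing dryness on another anti-VEGF could count as an event.

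**The case against.** Several objections stand, and they limit the point.

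- A reader might infer that the SAP certainly censors at treatment stop. It does not say so, and the protocol uses the phrase for study withdrawal.
- A reader might infer that persistent activity always ends treatment. The protocol's trigger is narrower, and other active eyes may stay on an 8-week interval. The 65% to 75% of patients implied to be active at Week 16 is therefore an upper bound on the pool for such stops, not an estimate of f.
- Fluid is only part of the trigger. Activity is the investigator's judgment, also covers BCVA loss, thickness, haemorrhage and sub-RPE fluid, and allows degenerative cysts. The OCT endpoint comes from the reading center, which does not assess activity (Protocol 8.3.1). Inflammation stops are not defined by fluid.
- Drying is not impossible once treatment is stopped: the ETD visit, 4 weeks after the last injection, still includes OCT.
- The event is first dryness at any visit, including Weeks 4 and 8, so d may be well above the Week 16 proxy and the excess smaller.
- SAP 2.7.1.2.3 already gives crude dry proportions by visit and over the whole study, and 2.7.1.2.4 tabulates numbers at risk and events.

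The last item is only a partial answer. The crude proportions give no time-to-event estimate, and the SAP does not say how stopped eyes enter the whole-study figure. None of these objections makes censoring at an activity-driven stop non-informative.

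**Conclusion.** The point holds as a correctable weakness in a descriptive analysis. The censoring term needs a definition. On the treatment-stop reading, one minus Kaplan-Meier is at or above the cumulative incidence of first dryness on brolucizumab. The direction is certain for that target. The size is not: d, f and g are all assumed, giving 1.3 to 22.5 points at d = 0.25–0.35 and less if more eyes dry early. The 17.5-point case needs half of the still-wet eyes to stop, which nothing in the documents supports, so it is a high scenario and not an expectation.

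Two stronger readings fail. The median is not always too early: it can shift only if fewer than half the eyes dry before the first activity-driven stops at about Week 14, and even then it may not move (first row of the table). Nor does the bias favour the drug for every target: for drying had treatment continued, it vanishes if stopped eyes would have dried at the same rate as the others.

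Priority is low to moderate. Time to dryness is not in Table 2-1, the study has one arm, and no test depends on this analysis.

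**What to change.** In SAP 2.7.1.2.4, and to match in 2.1.1:

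1. Define early discontinuation as discontinuation of study treatment.
2. Count dryness on OCT up to and including the ETD visit, before any other anti-VEGF, as an event.
3. Treat stopping without dryness by then, or death, as a competing event.
4. Report the Aalen-Johansen cumulative incidence of first dry retina with 95% CI (the event-code option in PROC LIFETEST). Give the median as the first week at which it reaches 50%, otherwise state that it was not reached.
5. Censor only eyes still on study treatment and not dry at EOS, or lost to follow-up.
6. Keep the Kaplan-Meier curve as supportive, labelled as assuming that stopped eyes would have dried at the same rate as eyes that continued.

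SAP 1.1 still describes a Q4 option after Week 8 that conflicts with the protocol's stopping rule. The two passages must be reconciled, because the share of eyes stopped depends on that rule.

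The cost is one SAP paragraph and one SAS option, with no new data. The reported dryness figure may become somewhat less favourable.
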